19.6 FUNCTIONAL TESTING PROTOCOLS

19.7 PATIENT INFORMATION FORM AND CONSENT

19.8 INTRAOP DATA COLLECTION FORM

19.9 DETAILED SURGICAL PLANNING

1. Introduction

Total knee arthroplasty (TKA) is the most effective treatment for patients with symptomatic end-stage knee osteoarthritis that has not responded to appropriate non-operative management. The aims of TKA are to provide pain relief and improve function. Accuracy of limb alignment, implant positioning, and soft tissue balance after TKA are important prognostic factors that affect postoperative clinical outcomes and long-term implant survivorship. Published literature has shown between 80% and 90% of patients are satisfied following this procedure. (1,2)

To this end there are two much debated theories of postoperative alignment after TKA. In total knee arthroplasty with mechanical alignment the aim is to achieve neutral limb alignment. This was to optimise longevity of TKA and prevent early failure. Total knee arthroplasty with kinematic alignment aims to restore the patient's own pre-arthritic knee anatomy with more natural alignment and preservation of native function. Enthusiasts debate both theories and it is yet to be established whether one is superior to the other.

An issue with both of these alignment theories is that they are purely related to bony anatomy. Neither considers soft tissue tension or balance before the bony cuts are made. Once the bony cuts are made the soft tissue balance is assessed and ligaments released until the TKA is balanced to the surgeon's satisfaction. In an initial cohort study well over 50% of patients in both groups required soft tissue releases to balance the TKA if these alignment theories were strictly adhered to.

The accuracy of soft tissue balancing is surgeon dependent and there is evidence that even experienced knee surgeons are poor at manually determining if a knee is balanced (3). This becomes particularly important when considering over half of these procedures throughout the world are performed by surgeons who undertake less than 25 TKA per year.

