Limits are placed in Functional alignment to prevent the severely arthritic knee with attenuated ligaments being placed in extremes of alignment. Understanding the “safe zone” for functional alignment is important for patient selection, implant choice, extent of intraoperative deformity correction, and long-term follow up. Furthermore, some disease pathology such as bone tumors, previous trauma, and congenital deformities may be present in conjunction with the arthritic knee and will have altered the native alignment of the limb. In such cases, using functional alignment to reproduce the altered anatomical alignment and mechanical function may have a detrimental effect on knee mechanics and wear.

A preliminary series by the principal investigator involved 122 TKR with mFA and over 350 kFA aligned knees since the introduction of RATKA into my practice. In an initial cohort of patients with functional alignment substantial differences were seen in femoral and tibial component position depending on whether a mechanical or kinematic plan was used. The final HKA angle was not changed as the coronal limb alignment is dictated by the collateral ligaments. The femur was 2 degrees valgus and the tibia 4 degrees varus with the kinematic plan compared to a neutral femur and 2 degree varus tibia with a mechanical plan. These small changes in position effect the three-dimensional relationships of the implants with the soft tissues. The initial cohort showed improved outcomes with the KA plan. There were confounding factors in that the groups were sequential, with MA plan group forming part of the surgeon’s learning curve. For the planned study a KA plan will be used as superior results have been seen in this group in the initial series..

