3.4 Study population and groups

Patients with symptomatic knee osteoarthritis requiring TKA will be recruited from the [name] and [name] private rooms at Perth Hip & Knee Clinic. All patients will be screened for eligibility based on the predefined inclusion and exclusion criteria (section 5.1). Patients interested in participating in the study will be provided with an information leaflet and contact telephone number for further information (Appendix 19.7). Details of those patients expressing an interest to participate in the study will be recorded and then be forwarded to the Research Physiotherapist.

The Research Physiotherapist will telephone or meet with the patient to answer any additional queries and confirm whether or not the patient would like to participate in the study. More complex queries will be escalated to the Chief Investigator who will telephone the patient directly to discuss these issues further. Ideally, the time frame from the orthopaedic consultation to the decision to participate in the study will be approximately one week, which will give the patient sufficient time to perform further research, discuss study participation with family and/or friends, and contact the Research Physiotherapist for any additional information. This time frame may be shortened if a patient is agreeable with the study, due to patient flow and appointment availability at the consulting rooms. Contact details of the Research Physiotherapist and Chief Investigator are provided within the patient information leaflet.

If the patient agrees to participate in the study, the Orthopaedic fellow will randomise the patient into one of the two treatment groups. Patients allocated to mFA TKA will form the 'control group' whilst those allocated to kFA TKA will form the 'investigation group'. The method for randomisation is discussed in section 3.6. Written informed consent for both the operative procedure and inclusion into the study will be signed at the preadmission visit (Appendix 19.7). The procedure for obtaining written informed consent is discussed in more detail in section 5.

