3.6 Randomisation procedure

The system for randomisation will be the same throughout the study period and must be strictly adhered to. The following method will be used to allocate a trial patient to either the mFA TKA ('Control group') or to the kFA TKA ('Investigation group').

Randomisation will be carried out using a blocked effect. This method is designed to randomize subjects into two groups that result in equal sample sizes over time. The blocks will be small (n=4), and balanced within the predetermined group assignments, which will keep the number of subjects in each group similar at all times. There will be no stratification factors involved in the randomization as randomization will occur before the trial starts. Using a randomization website (www.random.org), a random number (between 1 and 100000) will be generated. This will form the "seed" number for the blocked randomization process. Using a randomization website (www.sealedenvelope.com) the randomization list will be created. Patients will be allocated in a sequential order of consent, strictly adhering to the allocation of groups. Screen shots of the randomization process and seed number will be taken throughout, and held from the CI to minimize randomization bias. The orthopedic fellow will then privately communicate to the CI the allocated group, to enable alignment and templating planning to be performed using the MAKO software. All patients and clinical staff recording the post operative clinical outcomes of interest will remain blinded to minimize performance and detection bias.

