3.7 Surgical Intervention: MA vs. FA TKA

All patients undergoing TKA will undergo preoperative CT scan of the leg to establish the extent of the disease process, determine bone resection, and plan implant sizing and positioning. The preoperative CT scan will be used to create individualized plans for achieving mechanical and kinematic alignment and stored within the robotic program that is used during the operative procedure. This will ensure that all implants and equipment for achieving either mechanical alignment or functional alignment are ready and available for use in theatre. These

plans will provide the initial point from which functional alignment will be achieved.

Following informed consent and randomisation into one of the two treatment groups, patients will undergo robotic-arm assisted TKA by one of the participating surgeons. Surgery in both groups will be undertaken through the standard anteromedial arthrotomy with positioning of reference pins in the femur and tibia for registration of the hip centre, ankle position and limb alignment. The femur will be prepared first in all operations. Cruciate retaining technique will be used in both groups. Interoperative requirement for a more constrained implant will result in exclusion from the study.

In MA TKA, tibial and femoral osteotomies in the coronal plane will be planned perpendicular to the tibial and femoral mechanical axes respectively to achieve neutral overall alignment. Soft tissue balance will be assessed and minor adjustments to bony alignment made to balance the knees with a maximal adjustment of two degrees valgus and two degrees varus of coronal alignment from neutral. Femoral rotation will be planned to surgical epicondylar axis and adjustments to rotation made to allow equal flexion and extension balance (to within 1mm). If balance can not be achieved within these boundaries then soft tissue release will be undertaken.

In the sagittal plane, 0-3 degrees of posterior tibial slope and 0-5 degrees of femoral component flexion will be used to optimise implant sizing whilst preventing notching. In the axial plane, the tibial component aligned to Akagi's line, which connects the medial border of the patellar tendon attachment to the middle of the posterior cruciate ligament.

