6.2 Endpoint Analysis

6.2.1 Primary Endpoint

The analysis of the per-protocol population will be considered the primary analysis. The differences

between the MA TKA and FA TKA groups will be analysed by calculating the difference from baseline, per patient, and a two-sided confidence interval for the difference between the changes from baseline will be calculated. This confidence interval will cover the true difference in the percentage change from baseline with a probability of 95%.

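### The reason given for not stratifying does not hold, and the primary analysis has no surgeon or baseline-FJS term; the test stays valid, but a cheap gain in precision and protection is missed

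*Combined protocol and SAP*

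**What the plan says.** - **Randomisation (3.6).** "There will be no stratification factors involved in the randomization as randomization will occur before the trial starts". A single list serves everyone: "The blocks will be small (n=4), and balanced within the predetermined group assignments", and "Patients will be allocated in a sequential order of consent, strictly adhering to the allocation of groups".
- **Surgeons (3.7, 3.4).** After allocation, "patients will undergo robotic-arm assisted TKA by one of the participating surgeons". The plural shows more than one operator. Section 3.4 recruits from two named sets of private rooms, so the intended surgeon should usually be known before allocation.
- **Primary analysis (6.2.1).** The two "groups will be analysed by calculating the difference from baseline, per patient", with a two-sided 95% confidence interval for the difference between arms. No covariate is named. Sections 6.2.2 to 6.4 add none; analysis of variance appears only among techniques that might be used for secondary endpoints.
- **The document's own view of the surgeon (1. Introduction).** "The accuracy of soft tissue balancing is surgeon dependent".
- **Data capture (Appendix 19.8).** The intra-operative form, as shown, has no field for the operating surgeon.

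**The concern.** The reason in 3.6 confuses when a list is made with how it is structured. Preparing allocations before recruitment is compatible with one blocked list per surgeon. The only argument offered against stratifying therefore fails, and no argument is offered for leaving surgeon out of the analysis.

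The protocol regards soft-tissue balancing as dependent on the operator, and it wants alignment to be the only difference between the arms. If surgeons differ in the FJS their patients reach, two things follow from an unstratified and unadjusted design. Between-surgeon variation stays in the error term. In the single trial that is run, a chance difference in surgeon mix also passes into the estimated treatment effect.

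**Working it through.** **Inputs from the documents.** 100 enrolled 1:1 and 45 completers per arm (3.5); blocks of 4 on one list (3.6); 12-point target, pilot SDs of 6 and 8, one-sided alpha 0.05, power 0.80, 10% dropout (6.1).

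**Assumptions, not in the documents.** Two surgeons; case split 50:50, 70:30 or 85:15; a gap of 5, 10 or 15 FJS points between surgeons. The text available did not include sections 3.2 and 3.3, so the number of surgeons and their caseloads could not be checked.

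**Which SD applies.** The plan's 100 reproduces only at the dropout step: 90 / 0.9 = 100. The pooled pilot SD is sqrt((36 + 64)/2) = 7.07. With it, n per arm = 2 x (1.645 + 0.842)² x 50 / 144 = 4.3, so 5 per arm. Working back from 45 per arm, the implied SD is 12 / (2.487 x sqrt(2/45)) = 22.9. That mismatch is a separate matter. Here it only means that both SDs have to be carried.

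**Chance imbalance.** The SD of the between-arm difference in one surgeon's share is sqrt(p(1 − p) x 4/100). A simulation of 100,000 block-of-4 lists agrees:

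| Split | SD (percentage points) | Trials with a difference of 10 points or more | 95th percentile of the absolute difference |
|---|---|---|---|
| 50:50 | 10.0 | 37% | 20 |
| 70:30 | 9.2 | 33% | 18 |
| 85:15 | 7.1 | 21% | 14 |

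**Shift in the estimate (imbalance x gap), 50:50 split.**
- One SD: 0.10 x 5 = 0.5 points; 0.10 x 10 = 1.0 point.
- 95% limit: 1.96 x 0.10 x 5 = 1.0; 1.96 x 0.10 x 10 = 2.0.
- With a 15-point gap the 95% limit is about 3 points. At 85:15 the limits are 0.7, 1.4 and 2.1 for gaps of 5, 10 and 15.

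**Share of outcome variance at within-surgeon SD 22.9, 50:50 split.** A 10-point gap contributes 0.25 x 10² = 25, and 25 / (22.9² + 25) = 4.6%. A 5-point gap contributes 6.25, or 1.2%.

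**Effect of adding surgeon alone.** From 20,000 simulated trials of 90 analysed patients, 50:50 split, two-sided 0.05:

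| Within-surgeon SD | Gap | SE unadjusted | SE adjusted | Power for 12 points |
|---|---|---|---|---|
| 22.9 | 5 | 4.85 | 4.85 | 68.4% to 68.5% |
| 22.9 | 10 | 4.93 | 4.85 | 67.5% to 69.0% |
| 22.9 | 15 | 5.07 | 4.84 | 64.7% to 68.7% |
| 7.07 | 10 | 1.82 | 1.49 | about 100% both ways |

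For the 10-point gap the fall in SE is (4.93 − 4.85)/4.93 = 1.6%, about 2%, at SD 22.9, and (1.82 − 1.49)/1.82 = 18% at SD 7.07. A closed form agrees: sqrt(22.9² + 25) x sqrt(2/45) = 4.94 unadjusted, against 22.9 x sqrt(2/45) = 4.83 before the small loss from imbalance.

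**Validity.** Type I error of the planned unadjusted test was 4.8% to 5.3% in every scenario.

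**The case against.** The strongest reply is that nothing is broken. In an unstratified randomised trial the confidence interval already allows for chance imbalance in any prognostic factor, and the simulated error rate confirms it. The shift should also be read against the interval. With an SE of 4.93 the half-width is 1.96 x 4.93 = 9.7 points, so a 1 to 2 point shift at the 95% limit is small. This stands.

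It is also fair that the surgeon gap, the number of surgeons and the split are all assumed, and that the even split is the least favourable of those tried. Both arms use robotic assistance, one implant system, numeric balancing limits and standard aftercare, which should narrow differences between surgeons. These points stand too.

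Three stronger readings are tempting, and the documents do not support them.
- **That the result would be biased.** Chance imbalance adds variance. It does not favour either arm.
- **That the pilot shows surgeons differ.** The Introduction describes the sequential cohorts "with MA plan group forming part of the surgeon’s learning curve". That is one surgeon's change over time, which concurrent randomisation in small blocks already addresses. It is not evidence of a gap between surgeons.
- **That the per-protocol primary set distorts surgeon mix.** Exclusions decided during surgery could do so, but nothing in the text shows that they would. The simulations do not cover that case.

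Adjusting for a factor that was not used in randomisation is a choice, not an obligation. What the objection leaves standing is that the term costs almost nothing and that the stated reason for not stratifying is wrong.

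**Conclusion.** The point holds as a cheap improvement, not as a flaw that threatens the trial. The reason in 3.6 is invalid, more than one surgeon operates, and 6.2.1 has neither a surgeon nor a baseline-FJS covariate. The planned comparison remains valid.

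Under the assumed equal split and 5 to 10 point gap, the benefit of a surgeon term is protection against a shift of 0.5 to 1 point (one SD) or 1 to 2 points (95% limit). The gain in precision is none to about 2% at an SD near 23, and about 18% for a 10-point gap at the pilot's pooled SD. The documents do not establish that surgeon is a strong predictor of FJS in this trial. These precision figures are for surgeon alone; any gain from baseline FJS is additional and was not estimated.

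**What to change.** 1. **Section 6.2.1.** Before the two-year data are analysed, state that the two-year FJS difference between arms is estimated, with its 95% confidence interval, from a linear model containing arm, baseline FJS and operating surgeon as a fixed effect. Say in advance how surgeons with very few cases are pooled. The surgeon term costs one or two degrees of freedom. Baseline FJS is already collected under Table 1.
2. **Data.** Confirm that the operating surgeon is recorded for every patient, and add a field to the Appendix 19.8 form or name the source record if it is not.
3. **Section 3.6.** Remove the stated reason for not stratifying. This corrects the text and changes no result. Separate lists per surgeon are probably no longer practical, because recruitment was due to finish in December 2021 and this version is dated 14 October 2021. If allocations do remain and are stratified, the surgeon term must be in the model. Stratifying without adjusting made the test conservative in simulation (type I error 1.7% at SD 7.07 and 4.7% at SD 22.9, for a 10-point gap).

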3.7 Surgical Intervention: MA vs. FA TKA

All patients undergoing TKA will undergo preoperative CT scan of the leg to establish the extent of the disease process, determine bone resection, and plan implant sizing and positioning. The preoperative CT scan will be used to create individualized plans for achieving mechanical and kinematic alignment and stored within the robotic program that is used during the operative procedure. This will ensure that all implants and equipment for achieving either mechanical alignment or functional alignment are ready and available for use in theatre. These

plans will provide the initial point from which functional alignment will be achieved.

Following informed consent and randomisation into one of the two treatment groups, patients will undergo robotic-arm assisted TKA by one of the participating surgeons. Surgery in both groups will be undertaken through the standard anteromedial arthrotomy with positioning of reference pins in the femur and tibia for registration of the hip centre, ankle position and limb alignment. The femur will be prepared first in all operations. Cruciate retaining technique will be used in both groups. Interoperative requirement for a more constrained implant will result in exclusion from the study.

In MA TKA, tibial and femoral osteotomies in the coronal plane will be planned perpendicular to the tibial and femoral mechanical axes respectively to achieve neutral overall alignment. Soft tissue balance will be assessed and minor adjustments to bony alignment made to balance the knees with a maximal adjustment of two degrees valgus and two degrees varus of coronal alignment from neutral. Femoral rotation will be planned to surgical epicondylar axis and adjustments to rotation made to allow equal flexion and extension balance (to within 1mm). If balance can not be achieved within these boundaries then soft tissue release will be undertaken.

In the sagittal plane, 0-3 degrees of posterior tibial slope and 0-5 degrees of femoral component flexion will be used to optimise implant sizing whilst preventing notching. In the axial plane, the tibial component aligned to Akagi's line, which connects the medial border of the patellar tendon attachment to the middle of the posterior cruciate ligament.

In kFA TKA, femoral and tibial osteotomies will be planned for equal bony resections from the femoral condyles to replicate the patients anatomy. In the coronal plane, the distal femoral resection will be 6.5mm from the subchondral bone of both medial and lateral condyles, with compensation for wear by adjusting the resection by 1-3mm. In the proximal tibia, there will be 7mm of resection from the subchondral bone from both the medial and lateral tibial plateau. In the sagittal plane, resection angle will be determined intraoperatively to closely match the native femoral flexion and tibial slope. In the axial plane, posterior femoral resection will be 6.5mm from the subchondral bone of both medial and lateral posterior condyles. Tibial rotation will be aligned to Akagi's line. Adjustments will be made to bony alignment to balance soft tissues within the boundaries of six degrees varus and three degrees valgus Hip-Knee-Ankle (HKA) alignment. Femoral component alignment will be limited to six degrees of valgus and three degrees of varus in the coronal plane. Tibial alignment will be limited to six degrees of varus and three degrees of valgus in the coronal plane. Combined flexion of the components will be limited to ten degrees of flexion. Only if balance can not be achieved within these boundaries will soft tissue release be undertaken.

In both groups, polyethylene thickness will be selected to maximise range of motion whilst avoiding hyperextension and ligament laxity. Tibial depth will be adjusted to maintain insert thickness between 9 and 14mm. Any TKA requiring a 16 mm or greater polyethylene insert thickness will be excluded from the study.

Patients in both groups will undergo the same inpatient and outpatient postoperative rehabilitation programme. Intra-operative data will be recorded using the surgical data form (Appendix 19.7). The only difference between the two treatment groups is that the control group will undergo MA TKA and the investigation group will undergo FA TKA.

3.8 Description of the device

The Stryker Triathlon (Stryker Navigation, Mahwah, NJ) cruciate retaining knee system with patellar resurfacing will be used in both groups. The femoral component will be un-cemented, patella and tibial components will be cemented. This implant and its surgical instruments are already in routine use for TKA at St John of God Subiaco Hospital. The surgical team are fully trained and experienced with the use of the instruments and surgical equipment for these implants.

All postoperative rehabilitation will follow Perth Hip and Knee Clinic standard practice at St John of God Subiaco Hospital for patients undergoing TKA. This will include a combination of inpatient and outpatient physiotherapy as required. Each patient will have standard radiographic and clinical follow-up. The required outcomes from these clinical and radiological assessments will be recorded in the follow-up investigator form at discharge.

